6.5.2 Qualitative interview

Additionally, participants will be asked to take part in a qualitative interview about their experiences of the intervention and of the study. This will occur at 5 months after baseline, at which point participants should have completed the intervention. Interviews will be guided by a semi-structured topic guide, which will include some predetermined questions but will also be open-ended and flexible in order to allow for the emergence of new themes during the interviews. We will investigate the acceptability of the modified VIPP intervention through addressing themes such as parents' expectations and experiences of the intervention, its appropriateness for their child's stage of development, what they found helpful or less helpful, and potential changes that could be made to improve their overall experience of the intervention. We will explore their opinions on the acceptability and feasibility of virtual intervention delivery. The interview will be designed to last approximately 30-60 minutes and will be audio tape recorded for subsequent transcription.

Clinicians delivering the intervention will also be interviewed after intervention delivery, to explore their experiences of benefits, challenges, feasibility, acceptability and suitability for babies aged 2 to 6 months.

6.7 Withdrawal criteria

Participants will be withdrawn from the study if:

- 1) They ask to be withdrawn
- 2) The Chief Investigator or the participant's mental health care clinician believe that participating in the study is causing the participant harm
- 3) The participant lost capacity to decide whether or not to participate in the study

Reason for withdrawal would be documented. No further data on that participant would be collected. Data collected on the participant up to the point of withdrawal would be retained and used.

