7.4 Subject population

Data from any participant recruited into the study will be analysed, regardless of whether they received any sessions of the allocated treatment (intention-to-treat analysis).

8 **MONITORING, AUDIT & INSPECTION**

The study will be subject to monitoring, auditing and inspection by the sponsor or the sponsor's delegated representatives and the relevant authorities responsible for each of the sites where the research will take place. The purpose of the monitoring is to ensure that the study is conducted in accordance with the authorised study protocol, the principles of GCP and all applicable regulations.

The sponsor and regulators will require access to the study site for these inspections which will be supervised by the site investigator(s). The inspection activities apply to the following, and associated. areas in order to:

- review the study master/site file (hard and soft copies);
- review the study participant consent forms;
- review research documents as approved by applicable regulatory body and those referenced in protocol;
- review participant facing, current and superseded versions;
- review study measures and assessments as completed by participants;
- view the storage facilities/spaces for research documentation (paper and electronic);
- review site delegation of duties log;
- review trial amendment log.

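### Section 6.7 merges stopping the sessions with leaving the study, so a mother withdrawn for suspected harm before 5 months has no 5-month data, including her own account of acceptability

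*Protocol*

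**What the plan says.** Protocol section 6.7 lists three grounds for withdrawal from the study: the mother asks to leave, she loses capacity, or, as the second ground, "The Chief Investigator or the participant's mental health care clinician believe that participating in the study is causing the participant harm". The same consequences follow in all three cases: "Reason for withdrawal would be documented", "No further data on that participant would be collected" and "Data collected on the participant up to the point of withdrawal would be retained and used".

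Sections 6.5.1 and 6.5.2 place all post-baseline measurement at one time, 5 months after baseline. It comprises the questionnaires, the video rating of sensitivity, the therapeutic alliance questionnaire (mother and clinician versions) and the mother's qualitative interview. On the interview the protocol says: "We will investigate the acceptability of the modified VIPP intervention".

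Section 7.4 defines the analysis population: "Data from any participant recruited into the study will be analysed, regardless of whether they received any sessions of the allocated treatment", and labels this intention-to-treat. Section 7.1 (and section 3) adds that further mothers will be recruited if initial recruits stop the intervention early or are lost to follow-up. No section describes a route by which a mother judged harmed stops the sessions but stays in follow-up.

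**The concern.** Acceptability is part of the primary objective. In the Study Summary, primary outcome 4 is the alliance ratings and primary outcome 5 is participants' own accounts. Both depend on the 5-month contact, as does every pre-post change.

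A mother for whom the sessions went badly enough that staff withdrew her is the participant whose account would be most informative about acceptability. Under 6.7 her account is not sought, even if she would give it. The missingness is tied to outcome by rule, so the interviews, alliance ratings and pre-post changes tend to describe mothers who were not judged harmed. The harm is foreseeable: section 2.1 lists, as its first risk, mothers feeling criticised or judged, including while receiving video feedback.

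The results feed decisions. Section 7.3 uses the pre-post effect sizes in planning the sample size of the definitive trial, and uses the change in the percentage rated sensitive to check whether the adaptation has diluted the effect.

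**Working it through.** **1. Plan's own figures.** N = 10 rests on precedent (section 7.1), so there is no calculation to reproduce. The earlier trial's VIPP arm went from 35% to 50% rated sensitive at 5 months (section 1): 50 − 35 = 15 points, which agrees with section 7.3. The protocol gives no harm-withdrawal rate.

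**2. Timing.** Six sessions every two weeks (section 3.1) span 5 × 2 = 10 weeks. The Study Summary allows 3 to 5 months of treatment, and 6.5.1 expects it to be finished by the 5-month assessment. A withdrawal prompted by the sessions would therefore normally come before that assessment. A withdrawal after it loses nothing.

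**3. What is lost and what is kept** for a mother withdrawn under the second ground before 5 months:

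| Item | Available? |
|---|---|
| Consent percentage | Yes |
| Initiation/completion percentage | Yes, as a non-completer if sessions were unfinished |
| Reason for withdrawal | Yes (6.7) |
| Baseline data | Yes, retained and used (6.7) |
| Clinician interview | Yes (6.5.2) |
| Alliance rating (primary outcome 4) | No |
| Her own interview (primary outcome 5) | No |
| 5-month questionnaires and video | No |
| Any pre-post change | No |

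**4. 6.7 against 7.4.** Section 7.4 says whose data are analysed; 6.7 keeps data up to withdrawal. Both can be followed to the letter. But a pre-post change needs a 5-month value, so that analysis covers assessed mothers only, whatever its label.

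**5. Effect on the change in percentage sensitive (illustrative).** Assume that all mothers start at 35%, assessed mothers reach 50%, a fraction h is withdrawn, and withdrawn mothers would have been at q% at 5 months. The change in all mothers is (1 − h) × 50 + h × q − 35.

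| h | q = 0 | q = 35 |
|---|---|---|
| 10% | 45.0 − 35 = +10.0 | 48.5 − 35 = +13.5 |
| 20% | 40.0 − 35 = +5.0 | 47.0 − 35 = +12.0 |
| 30% | 35.0 − 35 = 0.0 | 45.5 − 35 = +10.5 |

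Assessed mothers show +15 throughout. The overstatement runs from 15 − 13.5 = 1.5 points to 15 − 0 = 15 points.

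**6. The dilution check with paired data (illustrative).** Section 7.3 treats no increase, or a fall, as potential evidence of dilution. Suppose two of ten mothers are withdrawn, one rated sensitive at baseline, and neither would have been at 5 months:

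- all ten: 4/10 to 4/10, change 0, flagged;
- the eight assessed: 3/8 to 4/8, change 50 − 37.5 = +12.5 points, not flagged.

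**7. How often it could arise (assumed rates).** The chance of at least one harm withdrawal among ten is 1 − (1 − p)^10: 40% at p = 5%, 65% at p = 10% and 89% at p = 20%. These rates are not from the protocol.

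**The case against.** The strongest reply is that 6.7 may not cover the case at issue. The second ground is that staff "believe that participating in the study is causing the participant harm", which is about the study and not the sessions alone. Section 2.1 names being asked to take part in parent-focussed research as a source of distress alongside the video feedback, so the assessments may themselves be part of the harm. Elsewhere the protocol treats stopping sessions as different from leaving: 7.1 lists early discontinuation separately from loss to follow-up, and 7.4 keeps mothers who had no sessions. A mother who stops sessions but is content to stay need not be withdrawn.

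Part of this stands. Where the assessments contribute to the harm, stopping them is a reasonable consequence, and the fix must allow for it. But the distinction drawn in 7.1 and 7.4 is not carried into 6.7. A mother who stops for another reason can be assessed at 5 months, while one judged harmed cannot, whatever the source of the harm and whatever her wishes. That makes the loss selective.

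It is also fair to say that this is a ten-mother case series which disclaims causal inference (section 3), and that the illustration in step 6 needs two withdrawals, one of them a sensitive mother who deteriorates. Both limit the weight of the point. They do not remove it, because 7.3 still uses these changes for the dilution check and for planning the next trial.

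**Conclusion.** The point holds in a limited form and is worth correcting. Under 6.7 a mother withdrawn for suspected harm before 5 months has no alliance rating, interview or pre-post change. These are missing for a reason related to outcome. Replacement under 7.1 can restore the number assessed without restoring the missing experience. The intention-to-treat label cannot be met for pre-post outcomes.

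The size is unknown. The 1.5 to 15 points and the reversed dilution check rest on assumed withdrawal fractions and assumed outcomes in withdrawn mothers; they show what is possible, not what is expected.

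A reader might infer more, and the documents do not support it:

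- *That 6.7 contradicts 7.4.* Both can be followed literally; the conflict is practical.
- *That the acceptability results lose these mothers altogether.* They remain in the consent and initiation/completion percentages, their reasons are documented, and clinicians are interviewed.
- *That withdrawals alone create an apparent improvement, such as 5/10 at baseline becoming 5/9 or 5/8 with no mother changing.* That uses unmatched denominators, which 7.3 does not specify. In the same mothers it is 5/9 to 5/9 or 5/8 to 5/8, no change, and the check would flag it.
- *That the outcome of suspected harm goes unrecorded everywhere.* Section 6.7 limits research data only; usual services continue (3.1, 9.6).
- *That stopping data collection is wrong in itself.* It is expected when a mother asks to leave or loses capacity.

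**What to change.** Reconcile 6.7, 7.1 and 7.4 by distinguishing the end of the sessions from the end of data collection. Leave the decision on when a mother is withdrawn, or when her sessions stop, exactly as it is.

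- In 6.7, where only the sessions end and the mother remains willing, allow the already planned 5-month measures and interview to be offered, unless the assessments themselves are considered part of the harm. Keep the complete stop for mothers who ask to leave and for loss of capacity.
- In 7.1, state that a mother who is replaced stays in the recruited cohort and in the counts.
- In 7.4, state that pre-post results are based on assessed mothers, and report the number missing at 5 months with the reasons.

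The cost is protocol and information-sheet wording. No new visit or measure is needed. Some mothers will decline the 5-month contact, so the gap will narrow but may not close.

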6.8 Storage and analysis of samples

Biological samples will not be taken as part of this research.

STATISTICS AND DATA ANALYSIS

7.1 Sample size

The case series size of N = 10 mothers follows established good practice in carrying out case series in previous related research (ISRCTN10052006; Wilkinson et al. 2016) and in the wider literature, where case series usually have 10 or fewer participants with the average being 8 (Abu-Zidan et al. 2012). Additional mothers will be recruited should initial recruits discontinue the intervention prematurely or be lost to follow-up.

7.2 Planned recruitment rate

We plan to recruit from perinatal mental health in:

- 1) Central and North West London NHS Foundation Trust
- 2) East London NHS Foundation Trust
- Oxleas NHS Foundation Trust

Predicted consent rate: In our previous BOOST study in a related sample, 52% of mothers approached by their clinician about the study met eligibility criteria and gave informed consent to participate.

Predicted recruitment rate: We plan to recruit 10 mothers between July 2021 and October 2021 i.e. 2 to 3 women a month.

7.3 Analysis plan

Qualitative analysis. The interview transcripts will be analysed using thematic analysis (Braun & Clarke 2006), by a research assistant and by [name], a service-user researcher who has previously co-analysed the qualitative feedback interviews generated during BOOST. Analysis will be supported by NVivo coding software. We will use the findings to make judgements about intervention acceptability and feasibility for mothers and clinicians, any facilitators and barriers to this, and any further minor modifications to the protocol that may be helpful.

Quantitative analysis. We will establish objective indices of feasibility and acceptability by determining:

- 1) % of trained clinicians implementing at least 1 VIPP intervention case
- 2) % of mothers invited to participate who give informed consent to do so
- 3) % of mothers initiating and completing the VIPP intervention
- 4) mother and clinician ratings of the therapeutic alliance during VIPP

We will calculate effect sizes and standard deviations for improvement in maternal sensitivity, parenting stress, parental self-efficacy and the parent-child bond from pre- to post-intervention. We will then combine these parameters with data on older infants (6 months plus) from BOOST in order to calculate the sample size required in a definitive randomised controlled trial. Additionally, we will compare the obtained effect sizes to those obtained when using the standard VIPP protocol in this population during BOOST, to check whether there is any evidence that the changes to the intervention protocol have led to dilution of intervention effects. For instance, in the BOOST trial, the percentage of mothers receiving VIPP who were rated as sensitive increased by 15% from pre-post intervention; by contrast the percentage rated as sensitive in the control group who did not receive VIPP deteriorated by 17%. Thus if the percentage of mothers rated as sensitive does not increase, or deteriorates, from pre-post intervention using the adapted protocol, we will consider this as potential evidence that the adapted intervention effect has been diluted relative to the standard protocol.

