1 BACKGROUND

Between 10 and 20% of women develop a mental illness during pregnancy or within the first year after having a baby. Perinatal mental illness carries a total long-term cost to UK society of £8.1 billion for each one-year birth cohort (Bauer et al. 2014). Nearly three-quarters of this cost relates to adverse long-term impacts on the child rather than the mother, including mental health and behaviour problems. Negative impacts on child development are in part likely to stem from early difficulties in parent-infant interactions and relationships, that have been linked to maternal perinatal mental illness. In particular, mothers experiencing perinatal illness have been shown to find it harder to understand and respond sensitively to their infant's communication. Such difficulties have been linked in meta-analytic studies to early parent-child relationship problems and subsequent problems in children's socioemotional development (DeWolff & van lizendoorn 1997, Ranson & Urichichuk 2008). Birth to age three is a unique period of neuroplasticity, with neurogenesis in brain regions responsible for cognitive and emotional development beginning to rise rapidly at 6 months and peaking at 36 months, driven by early life experiences (Shonkoff & Phillips 2000, Siegel 2015). Intervening at this stage offers a critical opportunity to prevent the lifelong damaging effects of early problematic socioemotional experiences (Shonkoff & Phillips 2000). In line with this, the NHS Long-Term plan has identified increasing access to evidencebased care for women with moderate to severe perinatal mental health difficulties, including parent-infant interventions, and increasing support for children's mental health from birth onwards, as a priority (NHS 2019). Perinatal mental health services, which treat women with moderate to severe difficulties, are ideally placed to offer such interventions. However, the evidence base for implementing parent-infant interventions in NHS services is minimal. There are currently to our knowledge no published trials of such interventions in perinatal mental health services. Video feedback parent-infant interventions specifically target the types of problems with parentchild interaction that are believed to partially explain the link between perinatal mental illness and poor child outcomes i.e. mothers' ability to understand and respond sensitively to their infants' communication. Meta-analysis has shown that the most effective interventions for improving parental sensitivity incorporate direct feedback to the parent based on recording and playing back videos of parent-infant interaction (Bakermans-Kranenburg et al. 2003). Our team of applicants has recently successfully tested one such intervention – the video feedback for positive parenting intervention (VIPP)- in three perinatal mental health services in London (The BOOST trial, ISRCTN 10052006). Trials in other at-risk groups - mothers with bulimia nervosa, insecure attachment or low sensitivity, and infants with behavioural problems - have shown that VIPP is more effective than control treatments in improving parental sensitivity, reducing child behaviour problems, and improving child socio-emotional development (Kalinauskiene et al. 2009, Klein Velderman et al. 2006, Stein et al. 2006, Van Zeijl et al. 2006). Our team has recently completed the NIHR-funded BOOST trial: the first randomised controlled trial of this intervention in perinatal mental health services. This was a small feasibility trial in 34 women using perinatal mental health services. Uptake of the intervention was high, with 95% of women randomised to VIPP initiating the intervention and 75% completing all 6 sessions. Feedback from mothers receiving the intervention and from perinatal mental health clinicians showed that VIPP was received very positively. Mothers consistently told us that VIPP helped to give them a different perspective on their relationship with their child,

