
boosting their confidence in their parenting abilities, and giving them new insights into how to understand and respond positively to their children's communication. This effect was reflected in the quantitative data on changes in parental sensitivity in the intervention and control groups, as shown in Figure 1 in the attachment. Ratings of parental sensitivity were conducted based on analysis of video data by a psychologist who was blind to intervention allocation, with clear positive intervention effects. In the group who received VIPP, just 35% were rated as sensitive in their interactions with their children at baseline; this rose to 50% at the 5-month follow-up (postintervention) and 64% at the 8-month follow-up. By contrast, in the control condition mothers who did not receive VIPP, average levels of sensitivity dropped over time. Whilst 50% of control mothers were rated as sensitive in their interactions with their children at baseline, this dropped to 44.5% at the 5-month follow-up and 33.25% at the 8-month follow-up.

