3 STUDY DESIGN

Case series of N = 10 mothers using perinatal mental health services and offered our adapted version of VIPP. Case series are useful for establishing the feasibility of a novel or adapted intervention (Kooistra et al. 2009, Stewart et al. 2019). They are often used for piloting and gaining feedback on adapted versions of intervention protocols before moving to conducting a full randomised controlled trial. For instance in our previous study we piloted an adapted version of VIPP for parents experiencing personality-related mental health difficulties in 9 mothers, before moving to test it in a trial; and the ACORN study piloted an adapted version of the Towards Parenthood intervention in a small case series of pregnant women before moving to test it in a trial (ISRCTN10052006; Wilkinson et al. 2016). We will follow guidance on designing high quality case series by using a prospective design; clearly defining our population, intervention, outcomes, and follow-up; and not making causal inferences about the treatment effect (Kooistra et al. 2009). Our planned sample size of 10 follows established good practice in carrying out case series in previous related research (ISRCTN10052006; Wilkinson et al. 2016) and in the wider literature, where case series usually have 10 or fewer participants with the average being 8 (Abu-Zidan et al. 2012). Additional mothers will be recruited should initial recruits discontinue the intervention prematurely or be lost to follow-up.

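### Section 7.3 would size the definitive RCT using uncontrolled pre-post effect sizes from 10 mothers, which are not the between-arm difference that such a trial must detect

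*Protocol*

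**What the plan says.** Protocol section 3 describes the design: "Case series of N = 10 mothers using perinatal mental health services and offered our adapted version of VIPP". There is no comparator. Section 7.1 sets the size by precedent: "The case series size of N = 10 mothers follows established good practice in carrying out case series in previous related research". Section 3 also commits the study to "not making causal inferences about the treatment effect".

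Section 7.3 then plans: "We will calculate effect sizes and standard deviations for improvement in maternal sensitivity", with parenting stress, self-efficacy and the parent-child bond treated in the same way. The next sentence gives the use, which is to size the later definitive trial: "We will then combine these parameters with data on older infants (6 months plus) from BOOST in order to calculate the sample size required". The sentence after that plans a separate comparison with BOOST, to see whether the adaptations have weakened the effect.

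Section 1 describes BOOST as "the first randomised controlled trial of this intervention in perinatal mental health services", and adds: "This was a small feasibility trial in 34 women using perinatal mental health services". It gives the percentage rated sensitive in each arm at baseline, 5 months and 8 months.

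**The concern.** In section 7.3 the parameters to be combined are the single-arm pre-post effect sizes and SDs. A parallel-group trial is powered on the difference between arms. A 5-month change in one group also contains treatment as usual, recovery, infant maturation and regression to the mean. The protocol's own data show that change without VIPP is not zero: "in the control condition mothers who did not receive VIPP, average levels of sensitivity dropped over time".

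Using the pre-post change as the RCT's target effect would treat it as a treatment effect, which sits badly with the section 3 commitment against causal inference. At stake is the size of the later trial. If it is too small, it cannot answer the question; if it is too large, it recruits more mothers from a vulnerable group than it needs.

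**Working it through.** **Plan's own figure.** There is none to reproduce. N = 10 has no alpha, power, effect or precision target, and no RCT size is given. I assume two-sided 5%, 80% power and 1:1 allocation for the future trial.

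**Step 1. BOOST, percentage rated sensitive (section 1).**

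| Arm | Baseline | 5 months | Change |
|---|---|---|---|
| VIPP | 35 | 50 | +15 |
| Control | 50 | 44.5 | -5.5 |

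- Pre-post change with VIPP: 15 points.
- Difference in changes: 15 - (-5.5) = 20.5 points.
- Raw 5-month between-arm difference: 50 - 44.5 = 5.5 points, with baselines 15 points apart in the opposite direction.

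Section 7.3 sets the +15 beside a control deterioration of 17%. That figure matches only the 8-month control change (50 - 33.25 = 16.75), so the two time points differ.

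**Step 2. Implied n per arm.** With p̄ the mean of p1 and p2,

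n = [1.96·√(2p̄(1-p̄)) + 0.8416·√(p1(1-p1) + p2(1-p2))]² / (p1-p2)².

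- Pre-post, 35% v 50%: (1.96×0.6991 + 0.8416×0.6910)² / 0.15² = 169.3, so **170**.
- Difference in changes, 44.5% v 65% (44.5 + 20.5): (1.96×0.7039 + 0.8416×0.6888)² / 0.205² = 91.4, so **92**.
- Raw 5-month contrast, 50% v 44.5%: (1.96×0.7060 + 0.8416×0.7050)² / 0.055² = 1,292.2, so **1,293**.

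These figures show how far the answer depends on the contrast chosen. None is a recommended size.

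**Step 3. Precision of a standardised change.** The documents give no effect size, so I take d = 0.3, 0.5 and 0.8, with d the mean change divided by the SD of change. The 95% limits come from the noncentral t distribution: find the noncentralities that place t = d√n at its 97.5th and 2.5th percentiles, then divide by √n. The n per arm is 2(1.96 + 0.8416)²/d² = 15.70/d². This carries over to a two-arm trial only if that trial analyses change scores with the same SD.

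| Treated mothers | d | 95% CI | n per arm at d | n per arm across the CI |
|---|---|---|---|---|
| 10 | 0.3 | -0.34 to 0.93 | 175 | 19 to no finite n |
| 10 | 0.5 | -0.17 to 1.15 | 63 | 12 to no finite n |
| 10 | 0.8 | 0.07 to 1.50 | 25 | 7 to 3,713 |
| 27 | 0.5 | 0.10 to 0.90 | 63 | 20 to 1,738 |
| 30 | 0.5 | 0.12 to 0.88 | 63 | 21 to 1,165 |

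BOOST's arm sizes are not given. The 27 assumes equal arms (34/2 + 10); the 30 assumes about 20 mothers in the VIPP arm.

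**Step 4. Precision of the SD at n = 10.** The limits are √(9/χ²) with 9 df: √(9/19.02) = 0.69 and √(9/2.70) = 1.83 times the estimate. Required n scales with SD², so by a factor of 0.47 to 3.33.

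**Step 5. Small-sample bias.** The Hedges factor is J = 1 - 3/(4×9 - 1) = 0.914, so an uncorrected d from 10 mothers is about 9% too large (1/0.914 = 1.094). With 30 mothers, J = 1 - 3/(4×29 - 1) = 0.974, and the bias is about 3%.

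**The case against.** The strongest reply is that section 7.3 speaks only of combining and names no method. BOOST was randomised, so its control arm could supply the missing comparator, and the detail could sit in a statistical analysis plan that is not at hand. This stands in part. A reader might infer that effect sizes will be pooled across the two studies under one common effect; the text does not say so. Nor does combining the sources contradict the comparison planned in the next sentence. What the protocol does fix is that the uncontrolled pre-post effect size enters the calculation. A control change taken from BOOST would also describe the standard protocol in older infants.

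A reader might also infer that the RCT will be undersized, because part of the change is natural improvement. The documents do not support that direction. The only control data they give show decline, so on sensitivity the pre-post change (15) is smaller than the difference in changes (20.5). The raw 5-month contrast (5.5) points the other way, but it ignores the 15-point baseline imbalance in a trial of 34 women.

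The defence also rightly notes that the Study Summary already plans confidence intervals for the pre-post effects, and that consent, initiation and completion rates are already collected. RCT sizing is not a listed objective.

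**Conclusion.** The point holds in limited form, as something that should be fixed. Section 7.3 puts a quantity that is not a between-arm difference into the sizing of a between-arm trial and does not say how BOOST, including its control arm, enters. On the one outcome with control data, sizing on the pre-post change gives 170 per arm against 92 for the difference in changes, a ratio of about 1.8 towards oversizing. For the self-report outcomes there are no control data and the direction is unknown. Even with about 30 treated mothers, d = 0.5 is compatible with anything from 21 to 1,165 per arm.

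These sizes rest on the assumed alpha, power and allocation, on illustrative values of d, and on assumed BOOST arm sizes. That a pre-post change is not a treatment effect rests on none of them.

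A reader might go further and infer that N = 10 is wrong or that the study is compromised. Neither follows: 10 is acceptable for a feasibility case series, the primary aims are feasibility and acceptability, and the sizing is a later calculation that can still be changed.

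**What to change.** Amend section 7.3 as follows.

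- State that the definitive RCT's target difference will be a justified minimum important difference. Any plausibility check should use BOOST's randomised contrast, adjusted for baseline, at one stated time point and with its confidence interval. The raw 5.5-point contrast is too weak an anchor.
- For the sample size calculation, take from BOOST-2 only the outcome SD with its uncertainty, the pre-post correlation, and the consent, initiation and retention rates. Which SD limit to plan on is a matter of choice, but it should be stated.
- Say how BOOST data, including the control arm, enter the calculation.
- Report the pre-post effect sizes descriptively, with the confidence intervals already planned and a small-sample correction, and do not use them as the RCT's target difference.

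The cost is a few sentences of protocol wording, slightly more work at the planning stage, and possibly a different stated RCT size. Recruitment, procedures and measures do not change.
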